6.10.1.2.4. C-cell Hyperplasia and C-cell Neoplasms

Treatment-emergent AESIs of C-cell hyperplasia and neoplasms will be identified using an LSC by HLTs of thyroid neoplasms, thyroid neoplasms malignant, and thyroid disorders. The summary report by treatment will be produced only if $\geq 1\%$ of patients have any of these AESIs.

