9.2.2.4. C-Cell Hyperplasia and C-Cell Neoplasms

Individuals with personal or family history of certain thyroid or nonthyroid endocrine abnormalities or certain preexisting laboratory and genetic characteristics will be excluded from the study (see Section 6.2). Patients with a personal or family history of MTC or personal history of multiple endocrine neoplasia syndrome type 2, or who have serum calcitonin ≥ 20 ng/L at study entry as determined by the central laboratory will be excluded. The assessment of thyroid safety during the trial will include reporting of thyroid treatment-emergent (TE) AEs (TEAEs) and measurements of calcitonin according to the Schedule of Activities (Section 2).

Patients who develop serum calcitonin increases $\geq 50\%$ of the screening value AND an absolute value ≥ 20 ng/L and < 35 ng/L at a postrandomization visit will be asked to repeat the measurement within 1 month. If this repeat value is increasing ($\geq 10\%$ increase from the initial elevated value), the patient will be encouraged to undergo additional endocrine assessment and longer-term follow-up by an endocrinologist to rule out a serious adverse effect on the gland.

Patients with an increase in serum calcitonin $\geq 50\%$ of the screening value AND an absolute value ≥ 35 ng/L at a postrandomization visit will be asked to immediately undergo additional endocrine assessments and longer-term follow-up by an endocrinologist.

For patients who require additional endocrine assessments due to increased calcitonin concentration per the criteria provided in this section or for thyroid-related TEAEs, data from the follow-up assessments will be collected on a specific eCRF.

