Table GBGL.1 shows the objectives and endpoints of the study.

Table GBGL.1. Objectives and Endpoints

Objectives	Endpoints

Primary To demonstrate that once weekly dulaglutide 4.5 mg and/or 3.0 mg is superior to dulaglutide 1.5 mg as measured by change from baseline in HbA1c at 36 weeks in patients with inadequately controlled T2D on concomitant metformin therapy.
	
 • The change in HbA1c from baseline

Secondary Efficacy: To demonstrate that once weekly dulaglutide 4.5 mg and/or 3.0 mg is superior to dulaglutide 1.5 mg for secondary efficacy parameters at 36 weeks (controlled for Type 1 error).
 
Safety: To compare each investigational dulaglutide arm (4.5 mg, 3.0 mg) to the 1.5 mg arm for selected safety parameters through 36 and 52 weeks (unless noted otherwise).
 
Pharmacokinetics (PK) and Pharmacodynamics (PD): To characterize dulaglutide PK and the dose and/or exposure-response relationships for key efficacy (eg, HbA1c and weight), and safety (eg, heart rate [HR]) endpoints.
	
 • The change in body weight from baseline • Proportion of patients achieving HbA1c target <7.0% (53 mmol/mol) • The change in fasting serum glucose (FSG) from baseline • Incidence of treatment-emergent adverse events (TEAEs) and discontinuation of study drug due to adverse events (AEs) • Adjudicated and confirmed cardiovascular and pancreatic AEs • Incidence of thyroid neoplasm AEs • Incidence of treatment-emergent (TE) dulaglutide anti-drug antibodies (ADA) and systemic hypersensitivity reactions • Changes from baseline in pulse rate • Electrocardiogram (ECG) parameters • Occurrence of hypoglycemic episodes • PK parameters (eg, maximum concentration [C_{max}], area under the curve [AUC]) at steady state • PD evaluations may include changes from baseline in HbA1c, body weight, and HR at Weeks 36 and 52

Objectives	Endpoints

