6.9.3. Planned Exploratory Analyses

Some of the planned exploratory analyses are described in Section 6.1. The remaining exploratory analyses are described in this section.

The analyses of proportions of patients reaching each target: HbA1c target $\leq 6.5\%$, body weight loss $\geq 5\%$, and body weight loss $\geq 10\%$ will employ the logistic regression model described in Section 6.1. The model for body weight target will be changed by replacing baseline HbA1c with baseline body weight as a covariate along with baseline HbA1c strata as a fixed effect. HbA1c target of the below 2 composite endpoints using LOCF will only apply a logistic regression model with an additional covariate of baseline body weight.

- HbA1c <7.0%, no body weight gain, and no documented symptomatic or severe hypoglycemia
- HbA1c <7.0%, body weight loss $\geq 5\%$, and no documented symptomatic or severe hypoglycemia

Longitudinal continuous variables (up to 52 weeks) such as HbA1c, body weight, FSG, and calcitonin will be analyzed using the MMRM described in Section 6.1. If the normality assumption is violated, an appropriate data transformation may be applied prior to analysis.

Nonlongitudinal continuous variables (up to 36 weeks) such as 6-point SMPG, C-peptide, fasting insulin, fasting glucagon, HOMA2-IR, and HOMA2-%B will be analyzed using LOCF by fitting a linear model with pooled country, treatment, and baseline HbA1c strata as fixed effects, and the corresponding baseline value as a covariate. A data transformation may be applied if data are not normally distributed.

The 6-point SMPG consists of measurements before and 2 hours after each of 3 meals within the same day. Each of the time points of the 6-point SMPG, mean of the premeal values, mean of the postmeal values, mean of all 6 time points, breakfast excursion, mid-day excursion, dinner excursion, and mean of all 3 excursions for each scheduled postrandomization visit will be summarized separately.

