6.10. Safety Analyses

The safety parameters to be analyzed include AEs, serious AEs (SAEs), AEs of special interest (AESIs), treatment-emergent AEs (TEAEs), safety laboratory analytes, vital signs, and electrocardiograms (ECGs). Adverse events of special interest are cardiovascular (CV) events, hypoglycemia and hyperglycemia, pancreatitis, thyroid C-cell hyperplasia and C-cell neoplasms, hypersensitivity reactions, injection site reactions, supraventricular arrhythmias and cardiac conduction disorders, acute gallbladder disease, and acute renal events.

All AEs will be coded using the Medical Dictionary for Regulatory Activities (MedDRA). Treatment-emergent AEs are defined as postbaseline events that are new events or preexisting conditions that worsened in severity after randomization using MedDRA term. The maximum severity level for baseline and postbaseline for each AE will be used as a criterion to determine TEAEs. If an AE occurs on the same date as the first dosing date with missing event occurring time, that event will be counted as a postbaseline event.

Unless otherwise specified, AEs will be reported using the MedDRA Preferred Term (PT) and/or System Organ Class (SOC). Selected AEs may be reported using MedDRA High Level Terms (HLTs) in addition to the SOC and PT, for consistency with other dulaglutide studies.

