6.10.1. Adverse Events

Summary statistics will be provided for the following data: medical history and/or preexisting condition AEs, TEAEs, treatment-emergent AESIs, and study and/or treatment discontinuations due to AEs or death. The numbers and proportions of patients experiencing each corresponding AE will be reported by treatment.

For each patient, the primary AE analysis will be summarized up to the end of the treatment period or premature termination of the study, whichever comes first.

As supportive analyses, SAEs, TEAEs, and treatment-emergent AESIs for each patient will be summarized through the end of the study, including the Safety Follow-up Period.

The incidence of patients with at least 1 TEAE will be summarized by PT and by treatment group, and also by the SOC and PT.

A summary of TEAEs by maximum severity will be presented descriptively by treatment group.

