6.10.1.1. Deaths, Other Serious Adverse Events, and Other Notable Adverse Events

All SAEs will be summarized by treatment by PT.

Patient listings for patient narratives will be generated.

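### Thyroid neoplasm AEs are a listed secondary safety endpoint, but no patient-level incidence is specified for them; the dedicated thyroid summary uses a wider event set and a 1% production rule

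*SAP*

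**What the plan says.** The secondary safety objective, worded alike in Table GBGL.1 of the protocol (section 4) and of the SAP (section 4), is to compare each investigational dose with 1.5 mg on selected parameters through 36 and 52 weeks. One listed endpoint is "Incidence of thyroid neoplasm AEs".

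SAP 6.10.1.2.4 is the AE section written for this topic. Its heading names C-cell hyperplasia and C-cell neoplasms, and its events are "identified using an LSC by HLTs of thyroid neoplasms, thyroid neoplasms malignant, and thyroid disorders". It continues: "The summary report by treatment will be produced only if" at least 1% of patients have any of these events. It gives no table layout and does not ask for the neoplasm terms to be counted on their own.

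Other thyroid outputs are planned:

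- SAP 6.10.1: the incidence of TEAEs "will be summarized by PT and by treatment group, and also by the SOC and PT", with no frequency threshold.
- SAP 6.10.1.1: "All SAEs will be summarized by treatment by PT".
- SAP 6.10: "Selected AEs may be reported using MedDRA High Level Terms (HLTs) in addition to the SOC and PT". This is optional, and thyroid is not named.
- SAP 6.9.3: "Longitudinal continuous variables (up to 52 weeks) such as HbA1c, body weight, FSG, and calcitonin will be analyzed using the MMRM".

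Protocol 9.2.2.4 takes a broad view of thyroid safety: "The assessment of thyroid safety during the trial will include reporting of thyroid treatment-emergent (TE) AEs (TEAEs"), together with calcitonin measurements.

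**The concern.** An endpoint stated as an incidence needs a rule for who counts as a case. Here the endpoint is thyroid neoplasm, while the only dedicated rule adds a high-level term (HLT), thyroid disorders, whose name is not limited to neoplasms. Followed as written, the plan gives either the incidence of a wider set or, below the 1% threshold, no dedicated table. In neither case does it specify the quantity named in Table GBGL.1.

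The topic is not incidental to this trial. A personal or family history of medullary thyroid carcinoma and raised calcitonin are exclusions (Protocol 6.2), C-cell hyperplasia or medullary carcinoma is a ground for permanent discontinuation of study drug (Protocol 8.1.1), and calcitonin is followed throughout (Protocol 9.2.2.4). A reader of the study report will look for a neoplasm count by arm and should not have to build it after the fact.

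**Working it through.** **Step 1. Endpoint against planned outputs.** The documents state no figure for this point, so the first check is a comparison of texts.

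| Output | Covers thyroid neoplasm AEs? | Patients with at least one neoplasm AE, by arm? | Always produced? |
|---|---|---|---|
| SAP 6.10.1.2.4 summary | Yes, within a wider set | Not specified | No, 1% rule |
| SAP 6.10.1 TEAE tables by PT and by SOC/PT | Yes, term by term | No | Yes |
| SAP 6.10.1.1 SAE table by PT | Serious cases, term by term | No | Yes |
| SAP 6.10 HLT reporting | Possibly | Only if chosen | No, optional |
| SAP 6.9.3 calcitonin MMRM | No, a biomarker | No | Yes |

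Rows by preferred term cannot safely be added up, because one patient may have more than one term. A system organ class total is wider than thyroid neoplasm. Elsewhere the SAP does ask for components to be shown apart: 6.10.1.2.9 separates acute from chronic renal failure, and 6.10.1.2.7 reports each event group separately by preferred term. Section 6.10.1.2.4 has no such instruction.

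**Step 2. The 1% rule.** Inputs: about 1800 randomized patients (SAP 5.2), 1% threshold (SAP 6.10.1.2.4). I read the threshold as applying to all arms together, as the wording suggests. 0.01 × 1800 = 18 patients. With X ~ Binomial(1800, p), the probability that the summary is produced is P(X ≥ 18):

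| Overall rate p of qualifying events (assumed) | P(X ≥ 18) |
|---|---|
| 0.3% | about 0% |
| 0.5% | 0.5% |
| 0.75% | 14% |
| 1.0% | 53% |
| 1.5% | 97% |
| 2.0% | more than 99.9% |

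The wider set makes the threshold easier to reach. Narrowing the set while keeping the rule would therefore make matters worse. With neoplasm rates of 0.2% on 1.5 mg and 1.0% on both higher doses, the overall rate is (0.2 + 1.0 + 1.0)/3 = 0.73%, and a neoplasm-only table under the rule would appear with probability 12%, despite a five-fold excess.

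**Step 3. What sharing a row would do.** The documents give no thyroid event rates, so every rate here is an assumption. Let the neoplasm rate be a on 1.5 mg and b on a higher dose, and let b₀ be a rate of other thyroid events equal in both arms. To a close approximation the ratio in a shared row is (b + b₀)/(a + b₀). For a = 0.2%, b = 1.5%, b₀ = 1%, this is 2.5/1.2 = 2.1, against 1.5/0.2 = 7.5 for neoplasms alone. Power is for the two-sided Fisher test at 0.05, 600 per arm, by exact enumeration, counting rejections toward excess on the higher dose:

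| a vs b | b₀ = 0 | b₀ = 0.5% | b₀ = 1% | b₀ = 2% |
|---|---|---|---|---|
| 0.2% vs 1.0% | RR 5.0, 28% | RR 2.1, 18% | RR 1.7, 14% | RR 1.4, 10% |
| 0.2% vs 1.5% | RR 7.5, 62% | RR 2.9, 41% | RR 2.1, 31% | RR 1.6, 22% |
| 0.2% vs 2.0% | RR 10.0, 85% | RR 3.6, 65% | RR 2.5, 52% | RR 1.8, 38% |

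The direction follows from the arithmetic whenever b₀ is positive and equal across arms. The size comes entirely from the assumed rates.

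**The case against.** Most of the strong form of this criticism fails. A reader might infer that thyroid neoplasms go untabulated, or that 6.10.1.2.4 is the SAP's only thyroid output. Neither is so: the general TEAE and SAE tables show every neoplasm term by arm with no threshold, and calcitonin has its own model.

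A reader might also infer that the plan pools neoplasms with other thyroid events and so dilutes a dose signal. Section 6.10.1.2.4 describes a search, not a layout. A summary broken down by HLT or preferred term would fit its wording. The contents of the sponsor's search category are not in the documents, so how many non-neoplastic terms enter is unknown. Dilution is thus conditional on both the layout and the background rate.

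The broad search also has a purpose. Protocol 9.2.2.4 calls for thyroid TEAEs in general, and C-cell hyperplasia, which is not a neoplasm, could be missed by a search on the two neoplasm terms alone.

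Finally, the trial was sized for HbA1c, and this endpoint lies outside the graphical testing scheme. A handful of thyroid cases would be read individually, so Fisher power is a weak measure of harm. The rates in step 3 that give appreciable power assume a 7.5- or 10-fold excess.

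All of this stands. It does not supply the missing item: a prespecified patient-level count for the endpoint that Table GBGL.1 names, shown whatever the number of events.

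**Conclusion.** The concern holds as a gap between a listed endpoint and its specified summary. The endpoint is narrower than the event set in SAP 6.10.1.2.4, no aggregate neoplasm incidence by arm is specified elsewhere, and the one dedicated summary is conditional on 18 of 1800 patients having a qualifying event. The production rule is the more tangible part: if qualifying events run at 0.5% overall, the summary is almost certain to be absent, and at 1.0% it is close to a coin toss. These probabilities assume about 1800 patients, a threshold applied across all arms, and rates that the documents do not give.

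Possible dilution is a secondary reason for the change and should be cited only as hypothetical. Primary and key secondary efficacy inference is untouched, and term-level data remain visible by arm. The correction is still worth making, because it lets the plan report its own endpoint at almost no cost.

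**What to change.** In SAP 6.10.1.2.4:

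1. Define the Table GBGL.1 endpoint as patients with at least one treatment-emergent event in the HLTs thyroid neoplasms or thyroid neoplasms malignant, reported by arm.
2. State that this row is produced whatever the event count, so that the 1% rule does not apply to it. Without this, splitting out the neoplasm terms could remove the table.
3. Compare each higher dose with 1.5 mg by Fisher's exact test, the SAP 6.1 default for categorical measures.
4. Show C-cell hyperplasia as a separate row.
5. Keep the three-HLT set as a supportive summary, in line with Protocol 9.2.2.4.

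The cost is a few sentences of SAP text and one or two extra table rows. No new data, assessments or coding are needed.

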6.10.1.2.5. Hypersensitivity Reactions

If $\geq 1\%$ of patients experience hypersensitivity reaction, a summary report will be generated by treatment. The hypersensitivity summary will be based on 3 SMQs: Anaphylactic reactions, Hypersensitivity, and Angioedema.

6.10.1.2.6. Injection Site Reactions

If $\geq 1\%$ of patients experience injection site reaction, a summary of events in the MedDRA HLT of Injection Site Reactions will be generated by treatment.

6.10.1.2.7. Supraventricular Arrhythmias and Cardiac Conduction Disorders

Summaries of each AESI will be produced separately by PT with decreasing frequency by treatment using SMQ.

The qualitative ECG data will be summarized by treatment separately for treatment-emergent abnormalities of conduction and rhythm.

6.10.1.2.8. Acute Gallbladder Disease

Summaries of all events of treatment-emergent biliary colic, cholecystitis, or other suspected events related to gallbladder disease will be generated by PT with decreasing frequency by treatment using SMQ.

6.10.1.2.9. Acute Renal Events

Summaries of all treatment-emergent renal safety events will be generated by PT with decreasing frequency by treatment separately for acute renal failure and chronic renal failure. To examine AEs indicating decrease in renal function, the SMQ for Acute Renal Failure and an LSC for chronic renal failure events will be used to search the clinical trial database for events of interest.

A summary and analysis using LOCF will be provided for renal functional laboratory measures: estimated glomerular filtration rate (eGFR) using Chronic Kidney Disease-Epidemiology Collaboration (CKD-EPI); eGFR using CKD-EPI cystatin-C equation (Inker et al. 2012); eGFR using CKD-EPI creatinine-cystatin-C equation (Inker et al. 2012); and creatinine, urine albumin/creatinine ratio (UACR), by treatment. The ANOVA model will be fit with treatment as a fixed effect on the ranked LOCF change from baseline data.

The minimum eGFR (CKD-EPI) value and the maximum creatinine, and UACR will be used for baseline and postbaseline calculations to generate the shift table. The shift table will use eGFR cutoffs (<30 , 30 to <60 , 60 to <90 , and ≥ 90 mL/min/1.73 m²); creatinine cutoffs ($\leq 1 \times$ upper limit of normal [ULN], $>1 \times$ and $\leq 2 \times$ ULN, $>2 \times$ and $\leq 4 \times$ ULN, and $>4 \times$ ULN); and UACR cutoffs (<30 , ≥ 30 , and ≤ 300 , and >300 mg/g).

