10.3.4.5. Laboratory Analyses

Laboratory safety measurements will be summarized. For continuous (numeric) laboratory analytes, the change from baseline by visit will be summarized as detailed in Section 10.3.1. Change from baseline to endpoint (LOCF) will be analyzed using an ANOVA on the ranks with treatment as a fixed effect unless otherwise specified. For subjective (qualitative) laboratory analytes, counts and percentages of patients with normal and abnormal values will be analyzed using Fisher's exact test.

Shift tables of the change from baseline value to the most extreme postbaseline value and from baseline to Week 52 for selected analytes using clinically meaningful thresholds will be summarized.

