
Tertiary/Exploratory
 
To compare once weekly dulaglutide 4.5 mg and 3.0 mg to the 1.5 mg arm as measured by the primary and secondary outcome measures at 52 weeks.
 
To compare once weekly dulaglutide 4.5 mg and 3.0 mg to the 1.5 mg arm for exploratory measures through 36 and 52 weeks (unless noted otherwise).
	
 • The change in HbA1c from baseline • The change in body weight from baseline • Proportion of patients achieving HbA1c target <7.0% (53 mmol/mol) • The change in FSG from baseline • Proportion of patients achieving HbA1c target ≤6.5% (48 mmol/mol) • Change from baseline in 6-point self-monitored plasma glucose (SMPG) profile • Proportion of patients achieving ≥5% body weight loss • Proportion of patients achieving ≥10% body weight loss • Proportion of patients meeting the composite endpoint of HbA1c <7.0% (53 mmol/mol), no weight gain, and no documented symptomatic or severe hypoglycemia • Proportion of patients meeting the composite endpoint of HbA1c <7.0% (53 mmol/mol), body weight loss ≥5%, and no documented symptomatic or severe hypoglycemia • Changes from baseline in fasting plasma glucagon, HOMA2-%B, HOMA2-IR, and C-peptide • Changes from baseline in serum cystatin C and cystatin C-based assessment of eGFR • Incidence of initiation of rescue therapy for severe, persistent hyperglycemia • Changes from baseline in systolic blood pressure (SBP), diastolic blood pressure (DBP), and rate pressure product (RPP) • Changes from baseline in serum lipid parameters (total cholesterol, high density lipoproteins [HDL], low density lipoproteins [LDL], very low density lipoproteins [VLDL], and triglycerides) • Diabetes Injection Device Experience Questionnaire (DID-EQ) scores at Week 12 • Changes from baseline in EQ-5D-5L scores • Changes from baseline in Impact of Weight on Self-Perception Questionnaire (IW-SP) scores • Changes from baseline in Ability to Perform Physical Activities of Daily Living (APPADL) scores

Objectives and Endpoints

Abbreviations: eGFR = estimated glomerular filtration rate; EQ-5D-5L = European Quality of Life 5–Dimension 5 Level; HbA1c = glycated hemoglobin A1c; HOMA2-%B = β -cell function as measured by the Homeostasis Model Assessment-2 method; HOMA2-IR= insulin resistance as measured by the HOMA2 method; T2D = type 2 diabetes mellitus.

[figure not shown]
5. Study Design

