The efficacy estimand analysis for a longitudinal continuous variable will employ a mixed-model repeated measure (MMRM) using restricted maximum likelihood to obtain model estimates with Kenward-Roger option to estimate denominator degrees of freedom. The model will include factors for treatment, pooled country, visit, treatment-by-visit interaction, and the baseline as a covariate. The observed margins option will be used in the LSMEANS statement whenever this option is allowed. For analyses of body weight and FSG, the baseline HbA1c strata ($\geq 8.5\%$ [69 mmol/mol] and $< 8.5\%$) will be added in this model as a fixed effect. An unstructured covariance structure will be used to model the within-patient errors. If this model fails to converge, the following covariance structures will be tested in order:

- toeplitz with heterogeneity
- autoregressive with heterogeneity, by visit
- compound symmetry with heterogeneous variances, by visit
- toeplitz
- autoregressive
- compound symmetry without heterogeneous variances, by visit
- compound symmetry

The first covariance structure that converges will be used.

The analysis model for nonlongitudinal continuous variables will be analysis of covariance (ANCOVA) coupled with imputation for missing endpoints unless otherwise noted.

For continuous laboratory measurements for safety, an analysis of variance (ANOVA) on ranks on change from baseline using last observation carried forward (LOCF) at Week 36 (Visit 9) and/or Week 52 (Visit 11) will be used with treatment as a fixed effect.

For all continuous measures, summary statistics will include number of patients, mean, SD, median, minimum, and maximum for both the actual and change from baseline values at each scheduled visit for each treatment unless otherwise specified. Least-squares means (LS means) and standard errors derived from the model will also be displayed for the change from baseline values at each scheduled visit for each treatment. Treatment comparisons will be displayed showing the treatment difference LS means and the 95% CIs between each investigational dulaglutide dose and dulaglutide 1.5 mg (treatment differences) at the same visit, along with the corresponding p-values.

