6.1.1. Adjustments for Covariates

The study is stratified by baseline HbA1c with country as a block factor; therefore, both stratification factors (baseline HbA1c $<8.5\%$ or $\geq 8.5\%$ and pooled country) will be fit in the corresponding statistical model as fixed effects for the non-HbA1c measurements unless otherwise stated. For analyses of HbA1c, the strata of baseline HbA1c will be replaced with the

covariate of baseline HbA1c. For other continuous variables other than some safety laboratory measures, a corresponding baseline measure will be added as a covariate.

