6.10.4. Clinical Laboratory Evaluation

Analyses of eGFR, creatinine, and UACR are described in Section 6.10.1.2.9. For other laboratory safety parameters, summaries will be provided in this section. For continuous (numeric) laboratory analytes, including serum lipid parameters (total cholesterol, high-density lipoprotein cholesterol, low-density lipoprotein cholesterol, very-low density lipoprotein cholesterol, and triglycerides), the rank of the change from baseline to endpoint (Week 36 [Visit 9] for primary DBL, Week 52 [Visit 11] for final DBL) will be analyzed as detailed in Section 6.1. For qualitative laboratory analytes, the numbers and percentages of patients with normal and abnormal values will be summarized by treatment.

Each pancreatic enzyme (pancreatic amylase [p-amylase] and lipase) and the maximum postbaseline value will be summarized by treatment in a shift table using $>1 \times \text{ULN}$ and $\geq 3 \times \text{ULN}$ separately for the Safety Population, Safety Population with normal baseline value, and Safety Population with baseline value $>1 \times \text{ULN}$.

An MMRM with pooled country, baseline HbA1c strata, treatment, visit, and treatment-by-visit interaction as fixed effects will be fit to analyze each pancreatic enzyme up to Week 52 (Visit 11). In this model, the log-transformed (post first dose measure/baseline measure) will be

the response variable, and log-transformed baseline measure will be used instead of baseline measure. The variance-covariance structure selection is detailed in Section 6.1.

An ANCOVA model for Week 36 (Visit 9) measurement using LOCF will be fit with the same model as the aforementioned MMRM but removing all terms containing visit.

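### The rank ANOVA of safety-laboratory changes omits baseline without giving a reason, which costs some precision; the HbA1c-subgroup model also drops continuous baseline, at a smaller cost

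*SAP*

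**What the plan says.** **Laboratory analyses.** Protocol 10.3.4.5 sets the model for numeric analytes: "Change from baseline to endpoint (LOCF) will be analyzed using an ANOVA on the ranks with treatment as a fixed effect unless otherwise specified". SAP 6.1 repeats it for continuous safety laboratory measurements at Week 36 and/or Week 52. SAP 6.10.1.2.9 applies it to three versions of eGFR, creatinine and the urine albumin/creatinine ratio (UACR): "The ANOVA model will be fit with treatment as a fixed effect on the ranked LOCF change from baseline data". SAP 6.10.4 sends "the rank of the change from baseline to endpoint" back to 6.1 for the remaining numeric analytes and names the lipids among them.

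**Covariate rule.** SAP 6.1.1 contains the exception: "For other continuous variables other than some safety laboratory measures, a corresponding baseline measure will be added as a covariate". It does not list the exempt measures or give a reason.

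**Where baseline is used.** SAP 6.9.3 analyses C-peptide, fasting insulin, fasting glucagon, HOMA2 and 6-point SMPG from LOCF data "by fitting a linear model with pooled country, treatment, and baseline HbA1c strata as fixed effects, and the corresponding baseline value as a covariate". On calcitonin it says: "Longitudinal continuous variables (up to 52 weeks) such as HbA1c, body weight, FSG, and calcitonin will be analyzed using the MMRM described in Section 6.1"; that MMRM carries baseline as a covariate. SAP 6.10.4 gives pancreatic enzymes an MMRM and a Week 36 LOCF ANCOVA, both with log-transformed baseline.

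**Subgroup.** SAP 6.12 and Protocol 10.3.6.2 remove continuous baseline HbA1c from the model when the HbA1c stratum (cut at 8.5%) is the subgroup. Here a reason is given: collinearity.

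**The concern.** Baseline is measured before the first dose for every analyte concerned, and it usually predicts change. Subtracting it does not use all of that information: unless baseline and endpoint are almost perfectly correlated, change still depends on baseline. Ranking deals with skewness but is no reason to leave baseline out, because a ranked baseline fits in the same model.

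The plan is also uneven. Lipids and the entry "Changes from baseline in serum cystatin C and cystatin C-based assessment of eGFR" are exploratory endpoints in SAP Table GBGL.1, alongside C-peptide, glucagon and HOMA2. The last three are baseline-adjusted and the first two are not. Within SAP 6.10.4 itself, pancreatic enzymes are adjusted while lipids are not.

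What is at stake is sensitivity. Comparing each higher dose with 1.5 mg on selected safety parameters is a stated objective, and an inefficient test makes a real shift in lipids or renal function easier to miss.

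For the subgroup, the collinearity is between stratum and continuous baseline. It widens the interval for the stratum main effect, but not for the randomized treatment-by-stratum contrast, which is the quantity of interest. Dropping baseline leaves the variation within each stratum unused.

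**Working it through.** **Inputs from the documents:** 510 completers per arm; SD of HbA1c change 1.1%; two-sided alpha 0.05 for treatment effects and 0.10 for interactions; stratum cut 8.5%. **Assumed, because the documents do not give them:** baseline-endpoint correlation ρ, skewness, size of laboratory shift, slope of HbA1c change on baseline, baseline HbA1c SD, and size of interaction.

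**1. The plan's own figure.** The only design calculation is for the primary endpoint. Power = Φ(0.22 / (1.1 × √(2/510)) − z). This gives 83.0% at two-sided 0.025 (the initial share of each dose) and 89.1% at 0.05, so the stated 80% or more is met. No figure is given for the laboratory or subgroup analyses.

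**2. Laboratory, closed form.** With equal variances at baseline and endpoint, Var(adjusted) / Var(unadjusted change) = (1 + ρ)/2.
- ρ = 0.5: 0.75, SE ratio √0.75 = 0.866
- ρ = 0.7: 0.85, SE ratio 0.922
- ρ = 0.9: 0.95, SE ratio 0.975

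A contrast with 80% power unadjusted would have 89.9%, 86.0% and 82.0% respectively.

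**3. Laboratory, simulation of the rank model.** There were 3,000 replicates per setting with 510 per arm. Baseline and endpoint were bivariate normal, or exponentiated with log SD 0.4, 0.8 or 1.2 (the last resembling UACR). The shift was 0.15 SD on the normal or log scale. Ranked change was tested without and with ranked baseline. Power (%), two arms:

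| ρ | Normal | log SD 0.4 | log SD 0.8 | log SD 1.2 |
|---|---|---|---|---|
| 0.5 | 64.0 → 75.3 | 63.8 → 74.0 | 62.5 → 69.1 | 59.3 → 67.2 |
| 0.7 | 85.4 → 90.3 | 85.1 → 89.2 | 82.8 → 86.4 | 79.0 → 82.8 |
| 0.9 | 99.7 to 100 for both models in all columns | | | |

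A three-arm version (middle dose at 0.10 SD) gave similar results, for example 64.7 → 76.0 for normal data at ρ = 0.5 and 57.2 → 64.5 at log SD 1.2. Over both versions the gain is about 7 to 11 points at 0.5 and 3 to 5 at 0.7.

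The sample-size equivalent is the squared ratio of the mean t statistics: 19 to 31%, 8 to 16% and 1 to 5% at ρ = 0.5, 0.7 and 0.9. A repeat with 2,000 replicates gave 20 to 28%, 9 to 17% and 1 to 5%. Type I error was 0.045 to 0.057 without baseline and 0.043 to 0.060 with it.

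**4. The ceiling at ρ = 0.9.** With a fixed 0.15 SD shift, power there is already near 100%, so no gain can show. A separate simulation (1,500 replicates) scaled the shift for a nominal 80%. For normal data, power was 78.5 → 87.8 at ρ = 0.5, 77.9 → 83.8 at 0.7 and 76.9 → 79.6 at 0.9. For lognormal data (log SD 1) it was 74.4 → 81.9, 70.5 → 74.9 and 71.1 → 71.5.

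**5. Subgroup.** This is a single-visit approximation to the MMRM with 2 × 510 patients. Baseline HbA1c was normal around 8.6%, truncated to 7.0–11.5%, with SD after truncation of 0.59 or 0.79. That puts 56 to 57% at or above 8.5%, and the cut carries 63 to 64% of baseline variance (variance inflation factor about 2.7 to 2.8). Residual variance with baseline in the model is 1.1² − slope² × baseline variance. Without it, slope² × within-stratum baseline variance is added.

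Example at SD 0.59, slope −0.5. Residual: 1.21 − 0.25 × 0.349 = 1.123. Added: 0.25 × (1 − 0.635) × 0.349 = 0.032. The increase is 2.8%, or 2.7% when each stratum has its own within-stratum variance.

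| Slope | Rise in interaction variance | Power with → without, SD 0.59 | Power with → without, SD 0.79 |
|---|---|---|---|
| −0.3 | 0.9–1.6% | 57.0 → 56.7 | 57.9 → 57.3 |
| −0.5 | 2.7–4.9% | 58.8 → 57.8 | 61.2 → 59.4 |
| −0.7 | 5.8–11.1% | 61.6 → 59.5 | 66.9 → 62.9 |

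Power is for a true interaction of 0.25 at alpha 0.10.

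**The case against.** The plan is internally consistent on this point. The protocol and three SAP sections agree, SAP 6.1.1 announces the exception, and a treatment-only rank ANOVA in a randomized trial holds its error rate. It is therefore a choice rather than a mistake. Validity and consistency stand, and they are why the point is minor. They do not supply a reason for leaving out a covariate that is already collected.

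Efficacy and safety sections often follow different conventions, and the adjusted models in SAP 6.9.3 also include country and HbA1c stratum, which this fix does not add. That is true. But pancreatic enzymes are adjusted inside the safety section, so the split does not follow that line, and baseline is the term most likely to carry information.

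Safety conclusions also draw on shift tables, treatment-emergent abnormal values and adverse-event searches, so little may hang on one p-value. That stands and limits the consequence. It does not argue for a less sensitive test.

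The size is hypothetical. The largest gains belong to the lowest correlation tried, and no affected analyte is shown to be there. This also stands: for stable analytes with ρ of 0.9 or more, the benefit is a few points at most.

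On the subgroup, a reason is given, the analysis is optional and the loss is small. All three hold. Centring baseline within stratum removes the stated reason, so the edit is still worth making if the analysis is run.

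**Conclusion.** The concern holds, as a low-severity improvement. The rank ANOVA is valid but less precise than it need be, and neither document explains why baseline is left out. At moderate correlation (0.5, assumed) the loss equals roughly a fifth to a third of the sample size. At 0.7 it is about 8 to 16%, and at 0.9 it is 1 to 5%. The apparent absence of gain at 0.9 in the fixed-shift simulation is a power ceiling.

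The point covers only analytes tested by rank ANOVA: the renal measures, lipids and other numeric analytes without a separate adjusted model. The subgroup loss is smaller, at 0.3 to 4.0 power points across the assumed slopes and baseline SDs. The primary and key secondary analyses and Type I error control are untouched. Confidence in the exact size is moderate, because every correlation, slope and effect size is assumed.

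**What to change.** **Main change.** In SAP 6.1 and 6.10.1.2.9, add the ranked baseline value as a covariate next to treatment in the rank ANOVA, and state the same term in 6.10.4. In SAP 6.1.1, replace the open exception with: *for safety laboratory measures analysed by rank ANOVA, the ranked baseline value will be the covariate.* If the sponsor prefers the present model, one sentence of rationale in 6.1.1 would close the gap in explanation, though not the loss of precision.

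**Minor change.** In SAP 6.12, replace the collinearity sentence with: *when baseline HbA1c is the subgroup, continuous baseline HbA1c, centred at its mean within each stratum (<8.5%, ≥8.5%), is kept as a covariate.*

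**Cost.** One model term in three SAP sections, one clause in 6.1.1, one sentence in 6.12, and a short justification for departing from Protocol 10.3.4.5 and 10.3.6.2, by the route Protocol 10.3.1 provides for changes that do not alter a principal feature. SAP 6.13.1 has the safety interim analyses follow the SAP, so any DMC laboratory outputs still to be produced would need the same term. No new data or visits are required.
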